5.4 Progressive Loading

Phase	Weeks	Strategy
Adaptation	1-2	Slow controlled speed, emphasis on movement quality
Stabilization	3-5	Moderate speed, increase repetitions per bout for G2 and G3
Progression	6-8	Explosive speed (sit-to-stand and squat), optional weighted vest (2-4 kg) for G3 and G4

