1. ABSTRACT

Background: Exercise snacks have emerged as a promising strategy to improve physical function in older adults. However, the optimal fragmentation pattern (i.e., how to distribute a fixed daily volume of exercise across the day) remains unknown. Furthermore, the effects of resistance-based exercise snacks on cognitive function in pre-frail older adults have not been investigated.

Objective: To compare the effects of four different fragmentation patterns of a three-exercise resistance snack (sit-to-stand, squat, and heel raise) on lower limb strength, dynamic balance, and executive cognitive function in community-dwelling pre-frail older adults.

Design: Four-arm parallel-group randomized controlled pilot trial.

Participants: 60 community-dwelling pre-frail older adults (Fried Frailty Phenotype score 1-2, aged ≥ 65 years).

Interventions: All groups perform a fixed total daily volume of 15 repetitions per exercise (sit-to-stand, squat, and heel raise), resulting in 45 total repetitions per day. The only difference between groups is the fragmentation pattern:

- G1 (highly fragmented): 1 repetition of each exercise per bout, 15 bouts/day (~30 seconds per bout)
- G2 (moderately fragmented): 3 repetitions of each exercise per bout, 5 bouts/day (~90 seconds per bout)
- G3 (lowly fragmented): 5 repetitions of each exercise per bout, 3 bouts/day

(~2.5 minutes per bout)

- G4 (consecutive control): 15 repetitions of each exercise per bout, 1 bout/day (~7.5 minutes per bout)

The intervention period is 8 weeks.

Outcome Measures: Primary outcomes include lower limb strength (30-second chair stand test) and dynamic balance (Timed Up and Go test). Secondary outcomes include comprehensive physical function (Short Physical Performance Battery), executive function (Stroop Color-Word Test and Trail Making Test), and falls efficacy (modified Falls Efficacy Scale). Feasibility outcomes include adherence, acceptability, and adverse events.

Data Analysis: A 4×3 mixed ANOVA will be used to compare group differences. Effect sizes (Cohen's d , η^2) will be estimated to inform a future definitive randomized controlled trial.

Expected Results: This pilot trial will provide preliminary evidence on the dose-response relationship between exercise snack fragmentation patterns and both physical and cognitive outcomes in pre-frail older adults.

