2.4 Study Objectives

This study aims to:

1. Compare the effects of four different fragmentation patterns on lower limb function and executive cognitive function in pre-frail older adults
2. Explore the dose-response relationship between fragmentation pattern and intervention effects
3. Determine whether 15 repetitions per day is above, at, or below the minimal effective dose threshold for resistance-based exercise snacks

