5. INTERVENTION

5.1 Four-Group Design Overview

All groups perform a fixed total daily volume of 15 repetitions per exercise (sit-to-stand, squat, and heel raise), resulting in 45 total repetitions per day. The only difference between groups is the fragmentation pattern.

Group	Repetitions per Bout (per exercise)	Bouts per Day	Duration per Bout	Fragmentation Level
G1 (Highly Fragmented)	1	15	~30 seconds	Highest
G2 (Moderately Fragmented)	3	5	~90 seconds	Moderate
G3 (Lowly Fragmented)	5	3	~2.5 minutes	Lower
G4 (Consecutive Control)	15	1	~7.5 minutes	None

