5.3 Triggering Strategies

Group	Trigger Type	Specific Instructions
G1	Event-based	Perform one bout after each bathroom visit and after each time drinking water
G2	Fixed time points	Perform bouts at approximately 9:00, 12:00, 15:00, 18:00, and 21:00
G3	Fixed time points	Perform bouts at morning (9:00), noon (14:00), and evening (19:00)
G4	Fixed time	Perform the single daily bout at a consistent time (e.g., 10:00 AM)

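### Section 5.4 progresses repetitions in G2 and G3 only, and allows a vest in G3 and G4 only, which contradicts the fixed daily volume and the claim that arms differ only in fragmentation

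*Protocol*

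**What the plan says.** Section 1 of the protocol states: "All groups perform a fixed total daily volume of 15 repetitions per exercise". Section 5.1 repeats this, gives a total of 45 repetitions per day over the three exercises, and adds: "The only difference between groups is the fragmentation pattern". Both sections give the same schedule: G1 does 1 repetition in each of 15 bouts, G2 does 3 in 5, G3 does 5 in 3, and G4 does 15 in 1.

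Section 5.4 sets a three-phase progression. Speed changes apply to all arms. Two other elements do not:

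- Weeks 3-5: "Moderate speed, increase repetitions per bout for G2 and G3".
- Weeks 6-8: "optional weighted vest (2-4 kg) for G3 and G4".

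Section 5.3 ties bouts to the clock in G2 ("Perform bouts at approximately 9:00, 12:00, 15:00, 18:00, and 21:00"), gives G3 three clock times, and shows no reduction in either arm at any phase.

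Outcomes are measured at Weeks 0, 4 and 8 (Section 3). Section 10.2 compares arms with a 4 × 3 mixed ANOVA, Tukey HSD for pairs, and linear and quadratic contrasts. Objective 2 in Section 2.4 is: "Explore the dose-response relationship between fragmentation pattern and intervention effects".

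**The concern.** The design isolates fragmentation only if everything else about the exercise prescription is the same in all arms. Section 5.4 removes that equality from week 3 onward, in different arms for different elements. A site that follows 5.4 breaks a property that Sections 1 and 5.1 state as fixed. A site that keeps to 5.1 ignores 5.4. If a site cut bouts to offset the added repetitions, it would break the bout counts in 5.1 and change the fragmentation levels themselves.

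Both post-baseline assessments are exposed: Week 4 falls within the repetition phase and Week 8 at the end of the vest phase. Both primary outcomes (30-second chair stand and Timed Up and Go) are measured at both visits. A difference between arms could then come from fragmentation, extra repetitions or added load, and the analysis could not tell which. A larger sample would not help, because the confounding is part of the prescription. The adherence measure in Section 6.3 counts bouts, so extra repetitions would not show there.

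Objectives 1 and 2 and the effect sizes meant to inform a definitive trial are at stake. Recruitment, retention and acceptability can still be estimated.

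**Working it through.** **1. The plan's own figure.** Daily volume per exercise = repetitions per bout × bouts per day (Section 5.1).

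| Arm | Per exercise | × 3 exercises |
|---|---|---|
| G1 | 1 × 15 = 15 | 45 |
| G2 | 3 × 5 = 15 | 45 |
| G3 | 5 × 3 = 15 | 45 |
| G4 | 15 × 1 = 15 | 45 |

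The base schedule agrees with the stated 15 and 45.

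**2. Section 5.4 rules by arm** (repetition rise, vest): G1 (no, no); G2 (yes, no); G3 (yes, yes); G4 (no, yes).

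**3. Pairs of arms that differ by rule.**

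- Week 4, repetition rule only: G1-G2, G1-G3, G2-G4 and G3-G4, so 4 of 6. G1-G4 is unaffected. G2-G3 may also differ, depending on the unstated increments, so 4 is a minimum.
- Week 8, both rules, counted on prescription accumulated since baseline: 6 of 6. G1-G4 and G2-G3 differ by rule only through the vest, so with no vest use the count is 4 of 6.
- Section 5.4 does not say whether the higher repetitions continue after week 5. If they return to base, the prescription in force during weeks 6-8 differs in 4 of 6 pairs, all through the vest (G1-G3, G1-G4, G2-G3, G2-G4). The cumulative count stays at 6.

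**4. Size, by worked example.** The increment is not given. Assume the smallest whole rise, +1 repetition per bout for all three exercises, with bouts unchanged:

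- G2: (3 + 1) × 5 = 20 per exercise; × 3 = 60 per day; 60/45 = 1.33, or +33%.
- G3: (5 + 1) × 3 = 18 per exercise; × 3 = 54 per day; 54/45 = 1.20, or +20%.
- G1 and G4 stay at 45.

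At +2 per bout, G2 and G3 reach 75 and 63 per day; at +3, 90 and 72.

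With rises of a in G2 and b in G3, the two arms have equal volume only if 5(3 + a) = 3(5 + b), that is 5a = 3b. The smallest whole-number case is a = 3, b = 5, which gives 6 × 5 = 10 × 3 = 30 per exercise in both arms, twice the stated 15.

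**5. Alignment with the planned trend contrasts.** Code each rule 0/1 in order G1 to G4: repetition rise 0,1,1,0; vest 0,0,1,1. On arm order 1-4:

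- Quadratic (1, −1, −1, 1) with the centred repetition rule (−0.5, 0.5, 0.5, −0.5): r = −2/(2 × 1) = −1.00.
- Linear (−3, −1, 1, 3) with the centred vest rule (−0.5, −0.5, 0.5, 0.5): r = 4/(√20 × 1) = 0.89.

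The protocol gives no contrast scores, so orthogonal polynomials on other plausible scorings were also tried. The last column replaces the 0/1 code by the added volume per exercise in the +1 example (0, 5, 3, 0).

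| Scoring | Repetition rule vs quadratic, \|r\| | Vest rule vs linear, \|r\| | +1 example volume vs quadratic, \|r\| |
|---|---|---|---|
| Arm order 1-4 | 1.00 | 0.89 | 0.94 |
| Log repetitions per bout | 1.00 | 0.83 | 0.94 |
| Repetitions per bout (1, 3, 5, 15) | 0.87 | 0.74 | 0.69 |
| Bouts per day (15, 5, 3, 1) | 0.87 | 0.74 | 0.95 |

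On arm order or the log scale, the quadratic contrast is G2 and G3 against G1 and G4, which is exactly the split made by the repetition rule.

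**The case against.** The wording of the contradiction is not in dispute, and nothing elsewhere in the protocol reconciles it. The case on the other side is about how much follows from it.

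- **The contrast figures illustrate and do not measure bias.** The 1.00 treats the rise as equal in G2 and G3. Under unequal volumes it becomes 0.94 or 0.95 in three scorings and 0.69 in one. This stands. The overlap is still substantial in every scoring tried, and the contradiction does not depend on it.
- **The Week 8 count is conditional.** The rise is listed only under weeks 3-5 and the vest is optional. If repetitions revert and nobody wears the vest, no pair differs in the prescription in force at Week 8. This also stands, but 4 of 6 pairs would still have had different volumes during weeks 3-5, including at the Week 4 visit.
- **This is a pilot with an exploratory objective, and G1-G4, the two extremes, is untouched at Week 4.** That is true. Estimating between-arm effects is nevertheless a stated purpose, and an exploratory estimate still has to refer to the factor it is named after.
- **Objective 3 is a separate problem.** Every arm has the same prescribed daily dose, so correcting 5.4 would not place 15 repetitions relative to a threshold. The only effect of 5.4 here is that G2 and G3 would no longer be observed at 15.
- **Dropping the vest is not the only remedy.** One vest rule for all arms would also remove the arm-specific difference. That choice is clinical.

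**Conclusion.** The concern holds: the plan is wrong as written. Following Section 5.4 breaks the fixed volume and the sole-difference statement in Sections 1 and 5.1. By rule, at least 4 of 6 pairs of arms differ in volume at Week 4. All 6 differ in cumulative prescription by Week 8, two of them by rule only through the optional vest. The Tukey comparisons and polynomial contrasts would therefore mix fragmentation with volume and, where the vest is worn, with load.

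The counts assume that bouts stay as in Sections 5.1 and 5.3, since no reduction is stated. The volume figures (60 and 54 against 45 per day) assume one extra repetition per bout; the actual increment and its duration are unknown. The correlations assume the codings and scorings shown. This should be fixed before participants reach week 3, because no later analysis can separate the factors.

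**What to change.** **Preferred.** In Section 5.4, delete the repetition increase for G2 and G3 and drop the vest. The speed progression then remains, common to all arms, and repetitions × bouts stays at 15 per exercise per day for all 8 weeks. No pair of arms then differs in prescribed volume or load. If external load is wanted clinically, offer the vest to all four arms on one stated rule.

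**If arm-specific progression is needed.** Remove the fixed-volume and sole-difference statements from Sections 1 and 5.1. State the increments and how long they last in 5.4. Restate the objectives in 2.4 as comparing packages of fragmentation, volume and load.

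**In either case.** Make sure the exercise log in Section 9.1 captures daily repetitions, and vest use if kept, and report both by arm.

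**Related wording.** Section 5.3 gives G1 event-based cues ("Perform one bout after each bathroom visit and after each time drinking water") and the other arms fixed times. The sole-difference statement needs qualifying for this even after 5.4 is corrected.

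**Cost.** Wording in Section 5.4 alone, or in Sections 1, 2.4, 5.1 and 5.4 under the second option, and at most one or two log fields. No extra participants or visits. The protocol does not state enrolment status. If enrolment has begun, this is an amendment, and participants already past week 2 should be identified by the schedule version they followed.

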6. OUTCOME MEASURES

6.1 Primary Outcome Measures

Outcome	Measure	Time Points
Lower Limb Muscle Strength	30-Second Chair Stand Test (30-CST). Number of complete sit-to-stand repetitions within 30 seconds. Higher score indicates better strength.	Baseline, Week 4, Week 8
Dynamic Balance and Mobility	Timed Up and Go (TUG) test. Time (seconds) to stand from a chair, walk 3 meters, turn, walk back, and sit down. Shorter time indicates better balance and mobility.	Baseline, Week 4, Week 8

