5.2 Exercise Standardization

Sit-to-Stand:

- Starting position: Seated on a rigid chair (seat height 43-45 cm), feet shoulder-width apart, hands crossed over chest
- Movement: Lean forward → extend knees to stand → hold fully upright for 1 second → slowly sit back down
- Progression/regression: Hands on armrests (regression), seat height increase (regression)

Squat:

- Starting position: Standing, feet shoulder-width apart, hands on hips or holding chair back
- Movement: Keep back straight → bend knees and lower hips as if sitting back → thighs parallel to ground → stand up

- Progression/regression: Partial squat (regression), holding chair back (regression)

Heel Raise:

- Starting position: Standing, feet together, hands lightly holding chair back for balance
- Movement: Slowly raise heels to maximum height → hold for 1 second → slowly lower
- Progression/regression: Holding chair back with both hands (regression)

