6.2 Secondary Outcome Measures

Outcome	Measure	Time Points
Comprehensive Physical Function	Short Physical Performance Battery (SPPB). Composite score (0-12) based on standing balance (0-4), 4-meter gait speed (0-4), and 5-repetition chair stand time (0-4). Higher score indicates better function.	Baseline, Week 4, Week 8
Executive Function - Inhibition Control	Stroop Color-Word Test (SCW). Three parts: Word, Color, and Color-Word. Interference effect (SCW score ÷ Color score) is calculated. Lower values indicate better inhibition control.	Baseline, Week 4, Week 8
Executive Function - Cognitive Flexibility	Trail Making Test (TMT). TMT-A (numbers 1-25) and TMT-B (alternating numbers and letters). Difference (TMT-B minus TMT-A) is calculated. Smaller differences indicate better cognitive flexibility.	Baseline, Week 4, Week 8
Falls Efficacy	Modified Falls Efficacy Scale (FES). 16-item questionnaire (0-10 per item, total 0-160). Higher scores indicate better falls efficacy.	Baseline, Week 8

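### A between-arm difference in the 30-second chair stand cannot be attributed to strength alone, because the test counts a trained exercise whose repetitions per bout are the randomized factor

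*Protocol*

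**What the plan says.** Protocol section 6.1 names two primary outcomes. The one for lower limb muscle strength is the 30-CST: "Number of complete sit-to-stand repetitions within 30 seconds. Higher score indicates better strength".

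Section 5.1 makes the same movement part of the training in every arm: "All groups perform a fixed total daily volume of 15 repetitions per exercise (sit-to-stand, squat, and heel raise), resulting in 45 total repetitions per day". What separates the arms is how many of these are done per bout: 1 in G1, 3 in G2, 5 in G3 and 15 in G4, the last being called the consecutive control. Section 5.1 adds: "The only difference between groups is the fragmentation pattern".

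Section 5.2 describes the trained sit-to-stand, with arms crossed on a rigid chair, as "Lean forward → extend knees to stand → hold fully upright for 1 second → slowly sit back down".

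Section 5.4 then changes the prescription. In weeks 3-5, repetitions per bout go up in G2 and G3. In weeks 6-8, sit-to-stand and squat become explosive with no arm excepted, and a vest is optional in G3 and G4. G1 is never moved beyond one repetition per bout.

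Section 10.2 compares the arms by a 4 × 3 mixed ANOVA with Tukey comparisons and by linear and quadratic contrasts.

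**The concern.** Practice on the tested task is common in exercise trials and does little harm between arms when all arms share it equally, because it cancels. Here it need not cancel. The 30-CST asks for many rises in succession, and the number of rises done in one bout is the factor under study. G4 trains with 15 rises per bout; G1 never does more than one. Pacing, skill and tolerance of repeated rises may therefore be trained to different degrees along the randomized factor.

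No other outcome settles the matter. None measures force or torque. The SPPB includes a run of five chair stands, and the TUG, which involves one rise, is labelled balance and mobility. The protocol does not mention the overlap between training and test.

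At stake is what the pilot may conclude. A 30-CST trend favouring less fragmentation could appear with equal strength gains in all arms, and a real strength advantage of fragmented bouts could be hidden. Estimating effect sizes for a later definitive trial is a stated purpose of this pilot, so a 30-CST effect read as strength would be carried forward under that name.

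**Working it through.** **Inputs** (section 5.1)

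| Arm | Rises per bout | Bouts per day | Bout duration |
|---|---|---|---|
| G1 | 1 | 15 | 30 s |
| G2 | 3 | 5 | 90 s |
| G3 | 5 | 3 | 150 s |
| G4 | 15 | 1 | 450 s |

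**1. The protocol's own volume.** Rises per bout × bouts per day: 1×15 = 3×5 = 5×3 = 15×1 = 15 per day. Times three exercises: 45 per day in every arm. The stated figure reproduces. If bouts are daily for 56 days, each arm does 15×56 = 840 rises. The amount of practice of the movement is therefore equal under the base prescription.

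**2. What differs.** Rises per bout run from 1 to 15, a 15-fold contrast between G1 and G4.

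**3. Pace.** Seconds per repetition = bout duration ÷ (3 × rises per bout):
- G1: 30/3 = 10
- G2: 90/9 = 10
- G3: 150/15 = 10
- G4: 450/45 = 10

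Every arm averages 10 s per repetition, with any rest included. That is 30/10 = 3 repetitions per 30 s, and G4's 15 rises take about 15×10 = 150 s.

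**4. Back-to-back rises.** Count = (rises per bout − 1) × bouts per day × 56:
- G1: 0×15×56 = 0
- G2: 2×5×56 = 560
- G3: 4×3×56 = 672
- G4: 14×1×56 = 784

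These counts rest on three assumptions: daily bouts, each exercise done as a block, and the base prescription kept for all 8 weeks. The protocol does not fix the order within a bout; the name of the G4 arm suggests blocks. If the three exercises were alternated, no arm would do two rises in direct succession. Section 5.4 also ends the base prescription for G2 and G3 from week 3, so 560 and 672 do not describe the full 8 weeks, and G3 may then exceed runs of five. G1's zero holds under any order. Even as computed, the counts show mainly a step from G1 to the other arms, not an even gradient.

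**5. What the data in hand offer.** The SPPB is scored 0-12, of which the chair-stand item contributes 0-4. Without it, balance plus gait gives 12 − 4 = 8, a 0-8 subscore containing no chair rise.

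**6. Size.** The protocol gives no SD, expected effect or rehearsal gain, so no size in repetitions or SD units can be derived. As an illustration only, assume a rehearsal shift between two arms of 15, no strength difference, and an unadjusted two-sided 5% test (normal approximation):

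| Assumed shift (SD) | Probability of a significant result favouring the rehearsed arm |
|---|---|
| 0 | 2.5% |
| 0.2 | 8% |
| 0.3 | 13% |
| 0.5 | 28% |
| 0.8 | 59% |

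With 11 per arm the last four are 7%, 10%, 22% and 47%. Tukey adjustment would lower all of them. The 95% interval for a pairwise standardized difference has a half-width of about 1.96×√(2/15) = 0.72 to 1.96×√(2/11) = 0.84, so the pilot could not exclude a shift of this order.

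**The case against.** The best counter-argument is that the test does not reproduce G4's training. The 30-CST counts rises against the clock, while the trained movement has a one-second hold and a slow descent, and the stated durations imply the same slow average pace in every arm. The explosive phase is not limited to any arm. This stands as a limit on size: a near-zero rehearsal effect is compatible with the protocol. It does not remove the point. The averages include any rest, and in weeks 6-8, just before the final assessment, G4 may do up to 15 explosive rises in a bout and G1 one.

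A second argument is that the randomized comparison is sound in itself, and that the first objective in section 2.4 speaks of lower limb function, which chair-rise performance serves directly. That also stands. Only the strength label, in the abstract and in 6.1, is in question.

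A third is that the sentence in 6.1 merely gives the scoring direction, and that interpretation can be left to an analysis plan. But 6.1 itself names the construct as muscle strength, and that is the outcome 10.2 compares between arms.

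A reader might go further and infer that the 30-CST is biased towards G4 by construction, or that no difference in it can reflect strength. The documents support neither. Practice volume starts equal, test-speed rehearsal is not shown, block order is only implied, and the ambiguity runs one way: rehearsal could produce or enlarge an advantage of G4 over G1, or mask the reverse, but could not create an advantage of G1 over G4.

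**Conclusion.** The concern holds as a limit on interpretation. The 30-CST measures performance on a trained task, and the resemblance of training to test varies with the randomized factor. A difference or trend across arms, especially one favouring less fragmentation, is therefore not evidence of strength alone. The analysis remains valid for chair-rise performance, and a G1 advantage would not be explained by rehearsal.

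The firm quantity is the contrast of 1 against 15 rises per bout. It rests on section 5.1 for G1 and G4 and on section 5.4 leaving G1 unchanged. The size of any rehearsal effect is unknown; the probabilities shown follow from assumed shifts and are not estimates for this trial.

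A related contradiction also clouds the 30-CST. Section 5.1 states a fixed volume and a single difference between arms, whereas section 5.4 raises repetitions per bout in two arms and offers a vest in two. The two sections must be reconciled.

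**What to change.** - **Section 6.1:** describe the 30-CST as chair-rise performance, a trained task, and state that between-arm differences favouring the less fragmented arms are not interpreted as strength alone. Align the strength wording in the abstract.
- **Section 10.2:** add a supportive arm comparison of the SPPB balance-plus-gait subscore (0-8), reported beside the 30-CST and TUG. Attach no rule that results must point the same way: with 11-15 per arm and no true effect, each measure agrees in sign about half the time by chance.
- **Sections 5.1 and 5.4:** reconcile the fixed-volume and single-difference statements with the arm-specific progression, and state whether the exercises in a bout are done in blocks or alternated.

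The interpretive change costs a few sentences and one extra analysis of items already collected; it needs no new test, visit or participant. The price is a narrower claim from the 30-CST. Balance plus gait is not a strength measure, so the strength question itself stays open; only a strength test that is not a trained task would answer it, and that would mean an added assessment.
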